**Etude Papillon**

Phase IV prospective study evaluating the reactogenicity and immunogenicity (both humoral and cellular responses) and the safety of the 9valent vaccine against HPV (Gardasil9®Merck) in HIV-positive women aged 15-40 years with fully suppressed HIV viremia on combined antiretroviral therapy. After a first open phase evaluating tolerability of Gardasil9, women will be randomized between two different doses schedules: in the first schedule, women will receive 2 doses at time 0 and 6 months and a third dose between 18-48 months if their antibody levels are insufficient; the second schedule will be 3 doses at 0, 2 and 6 months. Primary outcome is the non-inferiority of the rate of seroconversion against each HPV vaccine genotypes in women seronegative at baseline after either 2 or 3 doses of vaccination (month 7). Secondary outcomes are rate of seroconversion after 3 doses if they have received a third dose, completion of vaccine schedule, vaccine safety, antibody titles, and induction of cellular immunity against HPV contained in the vaccine, incidence of cervical HPV infection and incidence of abnormal cytology after vaccination.

Date: 15/12/2023

Author: [name] and [name] [name]

Version: 7

NCT NCT03391921

EUDRACT 2018-000228-33

FAMHP: FADG/R&D/BEN/mmn

Centre de Référence SIDA

# **Prospective longitudinal study on immunogenicity, induction of cellular immune responses and safety of vaccination against HPV with the 9valent vaccine in HIV-positive women**

## **The Papillon study**

### **Executive summary**

#### **Design**

Phase IV prospective randomized study comparing the reactogenicity and the immunogenicity (neutralizing antibody titres against each HPV vaccine genotype) of the 9valent vaccine against HPV (Gardasil9®Merck) in HIV-positive women aged 15-40 years with fully suppressed HIV viremia on combined antiretroviral therapy receiving two different vaccination schedules: 0, 2 and 6 months or 0, 6 months and a third later booster if needed. The safety of the vaccination (local or systemic reaction and impact on HIV viral control and immunodeficiency level) will be assessed.

The cellular immune response will be assessed in a subgroup of patients.

#### **Inclusion criteria**

- HIV-positive woman
- Age 15-40 years
- Undetectable HIV viral load (VL) <400 cp/ml for at least 6 months (i.e: having at least two separate VL<400 cp/ml at 6 months intervals; the most recent VL <400 cp/ml may be the screening CV for the study).
- No planned pregnancy foreseen for the next 7 first months and use of contraception such as condom, hormonal contraception or intrauterine device
- IC signed

#### **Exclusion criteria**

- Previous hysterectomy or conisation
- Previous or current biopsy-proven cervical, vulvar or vaginal HPV-associated lesion defined as ≥CIN2, VIN2, VaIN2 or invasive carcinoma
- Previous vaccination against HPV (at least one dose)
- Ongoing or planned pregnancy foreseen in the next 7 months
- Other immunodeficiency conditions such as ongoing or previous (within 6 months) chemotherapy against cancer or chronic systemic corticosteroids treatment or immunosuppressive therapy after transplantation
- Any condition contraindicating intramuscular injection such as warfarin therapy.

## **Number of patients**

Study: 200 patients

First phase: open label: 3 doses of vaccine at 0, 2 and 6 months

Second phase (150 patients): randomized study comparing two arms:

- ARM A schedule of vaccination (75 patients): 0 and 6 months and a facultative later booster dose if antibodies level insufficient at month 7
- ARM B schedule of vaccination(75 patients): 0,2 and 6 months

Substudy on cellular immune responses in a subset of patients: 40 patients and separated informed consent

## **Amendment (December 2023) :**

**In order to investigate the role of basal immune activation on the seroconversion and long-term persistence of HPV-specific antibody responses, we wish to extend the follow up to the following time points :**

- **24 months**
- **36 months**
- **48 months**
- **60 months**

**After completion of the vaccine administration (2 or 3 doses).**

**Women included will be contacted in order to collect a serum sample and will sign a new informed consent. If the time point is exceeded, we will retrieved plasma samples collected during routine care for HIV viral load determination (stored at the AIDS Reference Laboratory-LHUB ULB).**

**Primary outcome**

Rate of seroconversion of neutralizing antibodies against each HPV vaccine genotypes namely 6/11/16/18/31/33/45/52/58 among women seronegative at baseline for HPV vaccine genotypes, by measuring neutralizing antibody against the 9 vaccine genotypes of HPV at baseline, month 7. Comparison of that rate at month 7 (non inferiority defined as at least 80% of seroconversion in ARM A).

**Secondary outcomes**

- Completion of vaccine schedule.
- Safety and clinical tolerance of the vaccine administration.
- Impact on T-lymphocytes CD4+ counts and HIV viremia at month 7.
- Rate of seroconversion of neutralizing antibodies against each HPV vaccine genotypes namely 6/11/16/18/31/33/45/52/58 among women seronegative at baseline for HPV vaccine genotypes, by measuring neutralizing antibody against the 9 vaccine genotypes of HPV at Month 18, **24, 36, 48 and 60** compared to baseline.
- Measure of neutralizing antibodies title against each HPV vaccine types at baseline, month 7 and 18
- Assessment of long term persistence of HPV-specific antibody responses at 24,36,48 and 60 months after completion of the last vaccine administration dose.
- The cellular immune response against HPV 16/18/31/52/58 will be assessed in a subgroup of patients (n=40, 20 in each arm) on PBMC samples tested. For this analysis, a separated IC should be first signed by the patient.
- Incidence and prevalence of HPV infections and of abnormal cervical cytology performed by cytology and PCR on cervical swab at baseline and 12 months after the end of vaccination.

## **List of abbreviation**

ACIP	Advisory Committee on immunization Practices	cART
cART	combined antiretroviral therapy	
CIN	Cervical Intraepithelial Neoplasia	
HR	high risk	
HRHPV	high risk HPV	
HG	high grade	
HGCIN	high grade cervical intraepithelial neoplasia	
HGVAIN	high grade vaginal intraepithelial neoplasia	
HGVIN	high grade vulvar intraepithelial neoplasia	
HIV	human immunodeficiency virus	
HPV	human papillomavirus	
IC	informed consent	
ICC	invasive cervical cancer	
NCI	National Cancer Institute	
PBMC	peripheral blood mononuclear cell	
VaIN	Vaginal Intraepithelial neoplasia	
VIN	Vulvar Intraepithelial neoplasia	
VLP	Virus-like particle	

## Rationale

In women, persistent infection with high risk (HR) Human papillomavirus (HPV) is responsible for the development of high grade cervical, vulvar or vaginal intraepithelial neoplasia (HGCIN, HGVIN, HGVAIN) and invasive cervical cancer (ICC). Worldwide, HPV 16 and 18 represent respectively 50 and 20% of all HRHPV genotypes responsible for ICC [1]. Prophylactic vaccination against HPV 16 and 18 in adolescent and young women aged 16-26 years has been shown to be highly efficient in preventing both infection with these genotypes of HRHPV and HPV-associated lesions such as HGCIN, HGVIN, HGVAIN due to vaccine types (prevention of >90%) [2-4]. Vaccination of women aged 26-45 years is also efficient with around 80% of prevention for both infections and lesions related to vaccine HPV types [5-6].

HIV-positive women are more frequently infected with persistent HRHPV and suffer significantly more from HPV-associated diseases such as ICC (6 to 10 times more frequent than in the general population) and precancerous lesions. Their dysplastic lesions are more severe and they have a worst outcome after treatment [7-8].

We have conducted a prospective longitudinal study on HRHPV infection and HPV-associated diseases in a cohort of almost 900 HIV-positive women living in Belgium. We found that HRHPV infection was highly prevalent (43%) with a high incidence of new infections (13/100 women-year) [9-10]; 28% had cervical intraepithelial abnormal cytology and 3% had HGCIN compared to respectively 6% and 1.2% in the general Belgian population. We also showed that the most prevalent HPV genotypes were HPV 52 (20%), HPV 18 (15%), HPV 31/35/51/58 (12% each) and HPV 16% (9.5%)[11]. This genotypic distribution is different from the general population and is attributable first to HIV-infection which is a known risk factor for more frequent infection with HPV other than 16 or 18 and second with the African origin of most women followed for HIV in Belgium (similar genotype distribution is found in women living in sub-Saharan African countries).

Immunogenicity of the prophylactic vaccines against HPV 16 and 18 has been evaluated in several studies including almost 700 HIV-positive female between 8 and 45 years [12-17]. Most studies were done with the quadrivalent vaccine against HPV 6/11/16/18 (Gardasil®Merck). These studies showed a high seroconversion rate >90% for all HPV vaccine types in particular in patients with high CD4 cell count or under combined antiretroviral therapy (cART). These studies showed also that the presence of antibodies (seropositivity) against all vaccine-types HPV before vaccination was present in only 4-5% of women (median age 21 and 36 years) which suggest that in most HIV-positive adult women, there could be a benefit to vaccinate and protect against the HPV genotypes not yet encountered [14, 16]. Moreover, in patients seropositive for one or several HPV vaccine genotype(s), vaccination was able to induce a significant increase in these antibody titles (by  $1.5 \log_{10}$  mMU/ml) [17].

The ideal timing for vaccination against HPV is during adolescence however most adult women followed for HIV today had no opportunity to receive these vaccines during adolescence. The ACIP (Advisory Committee on immunization Practices), the British HIV Association and the Belgian Superior Health Council are recommending to vaccinate adult HIV-positive women against HPV [18, 19, 20]. This is partially based on the excellent results of the registration studies for the three different vaccines which demonstrated high efficacy in women up to 26 years. It is also based on later studies performed in HIV-negative women between 24 and 45 years old which demonstrate very good efficacy (between 88 and 91%) in the prevention of a combined endpoint (including persistent HRHPV infection, which is the preceding stage before precancerous lesions, external lesions such as genital warts and CIN1 due to HPV vaccinal types) [4-5].

In the USA, the ACIP recommends vaccinating HIV-positive patients against HPV as soon as possible starting from 11 and up to 26 and in the UK up to 40 years.

In Belgium, there are currently three available vaccines against HPV: the bivalent vaccine against HPV 16 and 18 (Cervarix®GSK), the quadrivalent vaccine against

HPV 6/11/16/18 (Gardasil®Merck) and the new ninevalent vaccine against HPV 6/11/16/18/31/33/45/52/58 (Gardasil9®Merck) available since June 2016. They are reimbursed in girls aged 12-18 years but are very expensive for women of 19 years or more: a course of 3 doses costs between 207 (Cervarix), 355 (Gardasil) and 404 euros (Gardasil9) (prices on October 19th 2017).

We have shown that the bi- or quadrivalent vaccines would cover at best 30% of our patients because they are infected with HPV genotypes other than 16 and 18; in comparison, vaccinating with the ninevalent vaccine would cover up to 82% of these women because it includes 5 additional HRHPV genotypes more frequently retrieved in our patients [11]. Other authors have shown similar results either in CIN3 from HIV-positive women or in AIN3 in HIV-positive man from the USA [21-22].

No data on the immunogenicity or safety of the ninevalent vaccine in HIV-positive patients are available so far. As the HRHPV genotypes included in this vaccine could better cover our patients than the bi- or quadrivalent vaccines, studying the immunogenicity and the safety of this vaccine in HIV-positive women is thus essential.

Regarding safety, an analysis of seven trials over 15,000 individuals who received at least one dose of the ninevalent vaccine, showed that the most common adverse effects were mild or moderate injection site reactions (pain, erythema, and swelling), occurring slightly more frequently than with the quadrivalent vaccine. The frequency of systemic adverse effects (eg, headache, fever, nausea, dizziness) was similar to the quadrivalent vaccine. Serious adverse effects occurred in <0.1 percent [23,24].

Our objective is to provide data on the immunogenicity and safety of the ninevalent vaccine which has not yet been reported for HIV-positive women although they are at greater risk of HRHPV infection and associated cancerous diseases. Our results could impact not only on the management of the 5700 women living with HIV in Belgium [25] but also on the healthcare of millions across the world who still suffer

from an unacceptable rate of HPV-related cancer and precancerous lesions. In sub-Saharan Africa, ICC is the first most frequent cancers in HIV-positive young women (30-40 years) with an incidence of up to 450/100.000 women-year compared to 30-50 in Africa and 9 /100.000 women-year in Belgium, both in the general population [26].

We also aim to provide data on cellular immune response against HRHPV in HIV-positive women. Several studies in HIV positive patients have shown that HPV vaccination was able to increase the specific cellular immune responses against HPV such as a raise in CD4+ and CD8+ lymphocytes against HPV 16 and 18 [13, 15]. This analysis comparing the evolution between cellular immune response targeted to specific HRHPV genotypes before and after vaccination will be performed in a subset of 40 patients and will focus on the vaccine genotypes most frequently encountered in our cohort such as 16/18/31/52 and 58.

By December 2018, many questions have aroused about how many doses of vaccine against HPV should be given to be efficient. The registration studies for Cervarix and Gardasil were performed in the early 2000' with a three doses schedule (0, 1 or 2 and 6 months) based on previous [studies with](#) similar protein-based vaccine such as hepatitis B vaccine. However, all the vaccines against HPV are designed as virus-like particle (VLP) with unique immunogenic properties. Immunobridging studies have confirmed that a twodoses regimen (0 and 6 months) was as reactogenic (giving an antibody response in >95% of the vaccinated subjects that were seronegative at baseline) and as immunogenic (inducing an antibody response of the same magnitude) as a three-dose schedule in teenagers less than 15 years -old [27]. More recently several randomized-controlled studies have shown that one- versus two- versus three-doses schedule were equivalent in terms of clinical endpoint. The Costa Rica Vaccine Trial (CVT) and the Papilloma TRIal against Cancer In young Adults (PATRICIA Trial), both studies using bivalent vaccine, showed similar vaccine efficacy over four years among women who received one, two and three doses of the HPV16/18 vaccine, and stable antibody

responses have been observed throughout the seven years of follow-up accrued to date in CVT, suggesting durability of responses [28]. Additionally, 36-month preliminary analysis of a large, post-licensure trial of the quadrivalent vaccine in India showed similar protection against HPV16/18 cervical infection whether the women received one dose, two doses, or three doses [29]. However, vaccine recipients in these trials were not randomized to receive these fewer doses, and immunogenicity among one-dose recipients was lower than that observed following two- or three-doses, leading regulatory bodies to conclude that the level of evidence in support of single-dose HPV vaccination is insufficient to warrant changes in current recommendations for two- or three- dose schedules. Consequently, the American National Cancer Institute (NCI) has recently launched a large randomized study comparing the clinical efficacy of Cervarix in one or two doses to Gardasil9 in one or two doses.

Indeed, the possibility of giving less than three doses is important in terms of compliance to the full vaccination scheme, tolerability of the vaccine and last but not least in terms of costs which are important with these vaccines. In Belgium, these vaccines are not reimbursed after 18 years-old even in more fragile population such as HIV-positive persons and total cost for a three-dose vaccine is more than 400 Euros.

Up to now, there is no data for less than three doses in HIV-positive women or HIV-positive adolescents and all the recommendations from the European AIDS clinical society, or British HIV Association or American guidelines on HIV and on vaccination recommend a three doses schedules for HIV adolescent or adults.

In order to answer the question of whether a two-doses schedule is not inferior to a three-doses schedule in HIV-positive women, we propose to randomly evaluate the reactogenicity and the immunogenicity of 2 different vaccination schedules given according to randomization in HIV virally-suppressed women [under cART](#): Arm A would receive vaccination with 9valent vaccine at time 0 [and at month 6](#) and a later facultative booster if antibodies measurement at month 7 are insufficient. Arm B

would receive 9valent vaccine at 0, 2 and 6 months. We will measure the antibody responses in both arms at baseline and month 7 (one month after the second or the third dose) to determine if a good antibody response can be reached already after 2 doses or needs a third dose in ARM A.

Our study has started as a phase IV open study enrolling patients in March 2018 and vaccinating the first patient in June 2018: up to now, 42 women have received the first dose of the three-doses schedule (0,2 and 6) and 25 have also received the second dose at month 2. The intermediate evaluation shows that acceptability and tolerability are excellent. We did not encounter adverse event of moderate or severe grade.

We propose to continue the classical 3 doses schedule (0, 2 and 6 months) in the patients that have been already enrolled and to randomized all the new patients between ARM A and ARM B in order to continue our study as a randomized non inferiority trial including 150 patients (75 per arm).

### **Design of the study**

The study started as an open study to evaluate the reactogenicity, the immunogenicity and the cellular immune response against each HPV vaccine genotypes (6/11/16/18/31/33/45/52/58) at month 7 which will be one month after completion of a three doses schedule (0, 2 and 6 months) in women seronegative at baseline for these antibodies.

After the December 2018 amendment, the study will enter a second phase as a non-inferiority study with randomization between two arms:

- **ARM A: vaccination at time 0 and 6 month and a later facultative booster if needed according to month 7 antibodies measurement**
- **ARM B: vaccination at time 0, 2 and 6 months**
- **Amendment: Introduction of a third phase of the study**
- **At the time of the start of the Papillon study (June 2018), there was no experience nor publication of vaccination with Gardasil9 in women living**

**with HIV (WLHIV). We have then started our study by a first open label part including 45 patients to observe if tolerance and safety was equal to what was described in HIV-negative women. At the end of this open label part (from June 2018 to January 2019), our data on safety were reassuring and we proceeded to the randomized phase as described upper (from January 2019 to February 2021).**

- **Because of the SARS-CoV2 pandemic, the enrollment had been slowed down and by February 2021, we had randomized 102 WLHIV instead of 150.**
- **As we needed to end the study enrolment by September 2019 because of budget constraints, we have introduced an amendment to give two doses (as in ARM A) to all the patients enrolled from February 25th 2021.**
- **We plan to analyze the results in intention-to-treat on the randomized cohort (n=102), and in On-treatment on the whole cohort (n=169).**

Antibodies title peaks one month after last vaccine dose than decrease to a plateau and stabilize around month 12 after receiving the last dose. In this study, antibodies against HPV will be measured at baseline, month 7 (that is to say 1 month after receiving 2 or 3 doses depending in which arm the patient has been randomized to) and month 18 (or 12 months after receiving the second or third dose, reflecting the stabilized antibodies level. We expect that two doses of vaccine in HIV-positive patients with well controlled HIV viremia under cART for at least 6 months could induce seroconversion in at least 80% of the patients seronegative at baseline whereas the seroconversion rate is expected to be 95% after 3 doses according to previous studies using the quadrivalent vaccine in HIV-positive patients. We find a minimum of 80% efficacy in the two doses arm acceptable as in this arm the vaccine costs would decrease by 33%, administration will be easier, the risk of local reaction after injection could also be decreased and compliance with the whole vaccine administration could be improved.

Regarding the number of patients that should be enrolled in the study, we considered a sample size calculation based on the SAS 9.4 program for comparing two independent proportions (1:1 allocation in a non-inferiority trial) by a Pearson Chi-square test. If we consider 95% rate of seroconversion for ARM B (3 doses vaccines) and 80% for ARM A (2 doses vaccines) with a significance level test of 0.05 (alpha) and an 80% statistical power (Beta), we found that 60 patients per

arm would be needed (120 patients in total). We would then need in total 150 women to be randomized taking into account the possibility of follow-up lost.

The purpose of vaccinating women is to induce antibody response against each HPV genotype contained in the vaccine and in particular against the 7 high-risk genotypes that induces cancer. If, after 2 doses of vaccine (ARM A), the month 7 antibodies measure shows absence of seroconversion against one of the HPV genotypes contained in the vaccine, the participant will receive a third booster dose of Gardasil9.

In order to assess long term persistence of HPV-specific antibody responses, the follow up will be prolonged to the following time points after completion of the vaccine administration : 24, 36, 48 and 60 months.

The role of basal immune activation on seroconversion rate and long term persistence of antibody responses, will be assessed.

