### **Primary outcome**

The rate of seroconversion of specific neutralizing antibodies against each HPV vaccine genotypes (6/11/16/18/31/33/45/52/58) at month 7 (which will be one month after either two doses of vaccine in ARM A or completion of a three doses schedule (0, 2 and 6 months) in ARM B) in women seronegative at baseline for these antibodies. The measure will be performed on a 10 ml tube by cLIA technique in Merck laboratory (see material and methods) [30,31]. Non inferiority of ARM A compared to ARM B will be reached if for each HPV genotype contained in the vaccine, at least 80% of the patients have a seroconversion rate. **We will analyze the results in intention-to-treat on the randomized cohort (n=102), and in On-treatment on the whole cohort (n=169).**

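### The 80% power for 60 women per arm belongs to a test for a difference between 95% and 80%, not to non-inferiority, and Arm A is assumed to sit exactly at the pass mark

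*Protocol*

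**What the plan says.** The sample-size paragraph in the Protocol, Design of the study, describes a calculation for "comparing two independent proportions (1:1 allocation in a non-inferiority trial) by a Pearson Chi-square test". Its inputs are alpha 0.05, power 80% and these rates: "If we consider 95% rate of seroconversion for ARM B (3 doses vaccines) and 80% for ARM A (2 doses vaccines"). The result is 60 per arm: "arm would be needed (120 patients in total"). An allowance for dropout follows: "We would then need in total 150 women to be randomized taking into account the possibility of follow-up lost".

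The paragraph before it explains where the 80% comes from: "We find a minimum of 80% efficacy in the two doses arm acceptable". The same figure is the success criterion. The executive summary has "non inferiority defined as at least 80% of seroconversion in ARM A". The main Primary outcome section says "Non inferiority of ARM A compared to ARM B will be reached if for each HPV genotype contained in the vaccine", the 80% level is met, and it restricts the analysis to seroconversion "in women seronegative at baseline for these antibodies".

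The February 2021 amendment text, repeated in Design of the study and in Amendment after Coronavirus crisis, reports that 102 women were randomized rather than 150. It makes those 102 the intention-to-treat cohort. The sample-size paragraph was left unchanged.

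**The concern.** A non-inferiority calculation asks how likely the trial is to rule out an unacceptable deficit when the new schedule is in truth acceptable. It needs a margin and a plausible true rate on the acceptable side of that margin. This paragraph states no margin between the arms, names a test of equality, and enters for Arm A the very rate that the protocol treats as the limit. Power computed that way answers the opposite question.

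This is the protocol's only power statement for its primary question. A reader would take it to mean that, if two doses reach 80%, the trial has an 80% chance of confirming non-inferiority. If that is untrue, neither meeting nor failing the criterion can be interpreted from the stated justification. The figure also concerns a single proportion in all randomized women, while the criterion covers nine genotypes, each among women seronegative for it at baseline.

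**Working it through.** **Inputs from the Protocol, Design of the study.** Arm B 95%, Arm A 80%, alpha 0.05 (sidedness not stated), power 80%, 1:1 allocation, Pearson chi-square.

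**Step 1: reproduce the 60.** The uncorrected chi-square formula for a difference is

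n = [z(1−α)·√(2p̄q̄) + z(0.80)·√(p₁q₁ + p₂q₂)]² / (p₁ − p₂)²

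with p̄ = (0.95 + 0.80)/2 = 0.875. Then 2p̄q̄ = 0.21875 (root 0.4677) and p₁q₁ + p₂q₂ = 0.0475 + 0.16 = 0.2075 (root 0.4555).

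- One-sided 0.05: (1.645 × 0.4677 + 0.842 × 0.4555)² / 0.0225 = 59.05, so 60.
- Two-sided 0.05: (1.960 × 0.4677 + 0.842 × 0.4555)² / 0.0225 = 75.12, so 76.
- With continuity correction: 72 one-sided, 88 two-sided.

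Only the first gives 60, so one-sided testing is inferred. Power at n = 60 is then 80.6%. The step to 150 also reproduces: 60/0.80 = 75 per arm, a 20% loss. The arithmetic is right for the hypothesis tested, which is that the two rates are equal.

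**Step 2: power for non-inferiority at the same rates.**

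*Margin reading.* The implied margin is 95 − 80 = 15 points (inferred). The assumed true difference is also 15 points, so it lies on the boundary and power is about alpha at any n. Exact enumeration with the Newcombe interval gives:

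| Per arm | One-sided 0.025 | One-sided 0.05 |
|---|---|---|
| 60 | 2.5% | 5.0% |
| 51 | 2.6% | 5.1% |

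*Literal rule.* Success is taken as an observed Arm A rate of at least 80%, which is at least 48 of 60. Binomial probabilities at n = 60:

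| True Arm A rate | One genotype | All nine, if independent |
|---|---|---|
| 80% | 57.6% | 0.7% |
| 85% | 89.4% | 36% |
| 90% | 99.4% | 95% |
| 95% | over 99.9% | over 99.9% |

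The last column is the ninth power of the one before it. Independence is one extreme. With perfectly correlated responses the all-nine probability equals the one-genotype figure, so at a true 80% it lies between 0.7% and 58%. At 51 per arm (at least 41 of 51) the one-genotype figure at 80% is 55.6%.

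**Step 3: the cohort to be analysed.** The Randomisation section gives a block size of 6, and 102/6 = 17 blocks, so 51 per arm holds if every block was filled. Otherwise it is an assumption. The protocol's own one-sided difference test then has power Φ[(0.15·√51 − 1.645 × 0.4677)/0.4555] = 74.6%. The seronegative restriction lowers the numbers further. The protocol gives no seronegative fraction per genotype, so a range is assumed:

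| Seronegative (assumed) | Per arm | Power of the difference test |
|---|---|---|
| 90% | 46 | 71% |
| 80% | 41 | 66% |
| 70% | 36 | 61% |

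**Step 4: counter-check.** If both arms are truly at 95% and the margin is 15 points, one-genotype power at 51 per arm, one-sided 0.025, is 86% (Newcombe) or 92% (Wald). If Arm A is truly 90%, the Newcombe figure is about 42%.

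**The case against.** The strongest reply is that 60 is the correct answer for the test named, that enrolment has closed so the paragraph can no longer change the sample size, and that the trial may be large enough anyway. With both arms at 95% and a 15-point margin, the usual unpooled formula needs only 27 per arm (one-sided 0.05) or 34 (one-sided 0.025), fewer than 51. All of this stands. The fault is the hypothesis, not the sum, and no shortfall in power is shown for one genotype. But that adequacy rests on an Arm A rate well above 80%, which the protocol never enters, and nothing in that reading yields 60.

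A second reply is that the text expects at least 80% in Arm A, a floor rather than a best guess, so power at exactly 80% is low by construction. That is fair. The boundary figures do not predict this trial's power; they show that the printed 80% cannot be read as power for non-inferiority at the printed rates. Likewise, the independence figure for nine genotypes is only the extreme of a range, since the same women respond to one vaccine.

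Several inputs are inferred: sidedness, the margin, the equal split, the seronegative range, and the reading of the 80% rule as a point estimate. The main conclusion does not depend on sidedness: two-sided, 60 per arm would still be a difference test, with about 70% power. A non-inferiority calculation with both arms at 95%, a 10-point margin and one-sided 0.05 gives 59, but the protocol states neither that margin nor 95% for Arm A, so this near match is a coincidence.

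Finally, the shortfall to 102 is openly disclosed, and restated precision could sit in an analysis plan not seen here. That absence alone would not be a finding. What remains is that the current text presents a power figure for the wrong hypothesis and says 120 are needed beside an analysis cohort of 102.

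**Conclusion.** The concern holds. The stated 80% power at 60 per arm is for detecting that two doses are worse than three, at 95% against 80%. It is not power for non-inferiority. At the protocol's own rates, non-inferiority power is about 2.5% or 5% (inferred 15-point margin, one-sided 0.025 or 0.05), or about 58% for one genotype under the literal 80% rule. The calculation does not cover the nine-genotype requirement or the seronegative restriction, and it does not describe the 102 women to be analysed.

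This is a mis-stated justification, not proof of an underpowered trial. If two doses truly perform close to 95%, one-genotype power is adequate. If Arm A is nearer 90%, it is not, on a 15-point margin. The 51-per-arm split and the seronegative fractions are assumptions.

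**What to change.** Rewrite the sample-size paragraph in Design of the study:

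- Remove the claim that 60 per arm gives 80% power for non-inferiority. State that the original figure came from a one-sided 0.05 chi-square test for a difference between 95% and 80%.
- For the 102 randomized, report the expected confidence-interval precision (preferable now that enrolment has closed) or power, by one named method. Give the margin, one-sided alpha, assumed rates, all-nine rule and a range of seronegative fractions as labelled assumptions. For example, 48/51 seroconverting in each arm gives a 95% Newcombe interval of about ±11 points, and 34/36 in each arm about ±13 points.
- Mark any margin set now as defined after randomization ended.
- State that failing the criterion is inconclusive unless the interval itself shows inferiority.

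The cost is one paragraph. The stated power will look less favourable, and any added margin must be reported as post hoc. No further enrolment is proposed and the vaccination schedules are untouched.
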